The Use of Acthar (ACTH) in Patients with Focal Segmental Glomerulosclerosis (FSGS) Who Have Developed Chronic Kidney Disease Stage V (CKD) or End Stage Renal Disease (ESRD) and Are Undergoing a Renal Transplant

Principal Investigator: [name]., MPH
Ph. [contact]
Email: [contact]

COMIRB 17-2336

Version Date: July 11, 2018

I. Hypotheses and Specific Aims

This is an open-label pilot study where all subjects will be treated with the drug, Acthar. The specific aim is to determine the rate of recurrent FSGS through evaluation of kidney biopsies performed post renal transplantation. FSGS is a type of nephrotic syndrome that can recur aggressively after renal transplantation. When FSGS recurs after transplant it increases patient morbidity and increases graft loss.

It is believed that ACTH, besides steroid dependent properties, has steroid independent properties (see figure 1 on page 10). With the steroid independent properties it may stimulate the MCIR receptor which affects not only the podocytes, but also the T-cells, B-cells, NK-cells and APC-cells.

The primary end-point is to measure proteinuria prior (if patient still makes urine) and after renal transplantation and determine the change in proteinuria and the recurrence of FSGS as seen in kidney transplant biopsy. Kidney transplant biopsies will be performed at time 0 (at implantation), 3 months and 12 months post transplantation. Our hypothesis is that the use of Acthar, on patients with history of FSGS as cause of chronic kidney disease, at the time of renal transplantation and for a 6-month period of time following transplant, decreases the probabilities of patients developing recurrent disease after renal transplantation.

Our secondary end point is to evaluate renal function after transplantation as measured by eGFR. We hypothesize that patients will maintain a stable eGFR and creatinine while on Acthar and after it is stopped.

II. Background and Significance

Wait time for kidney transplantation is on average at least 5 years and unfortunately many patients die while waiting for kidney transplantation. Recurrent disease affects 23-30% of renal transplant recipients with FSGS. No

COMIRB 17-2336
P.I. [name]
Version 7-11-2018

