known genetic mutations have been identified among those with recurrence. Plasmapheresis has resulted in complete or partial remission in 75% of those with recurrence after transplant but this treatment is very aggressive as it increases bleeding risk and involves the placement of a catheter. Furthermore, it is performed usually three times a week for months in order to achieve remission. Modern immunosuppression does not reduce the rate of recurrent FSGS (1). Moreover, recurrence after transplantation, where the patient is already immunosuppressed, is a poor prognostic factor and it brings a high risk of graft failure.

Typically, recurrence of primary FSGS occurs early in the post transplantation period with heavy proteinuria and progressive renal insufficiency and graft failure. Current animal and human data suggest that primary FSGS is likely to be initiated by podocyte injury; however, Savin *et al.* (2) described a circulating plasma factor and its association with many cases of primary and recurrent FSGS. The rapid nature of recurrent FSGS after transplantation is consistent with the theory that one or more circulating factors may be playing a major role in the pathogenesis of recurrence (3).

Acthar is FDA approved for the treatment of nephrotic syndrome. The FDA package insert of Acthar: “To induce a diuresis or a remission of proteinuria in the nephrotic syndrome without uremia of the idiopathic type or that due to lupus erythematosus.” (3). It still has not been studied in renal transplant patients, but clinical data in our center has been very encouraging and it has been used safely and effectively in renal transplant recipients with FSGS.

This medication has been studied in nephrotic syndrome in native kidney disease. Most studies have used a dose of 80 units twice a week (one cc of the medication contains 80 units). There is no data on the renal transplant population, but is interesting to note that with the steroid independent properties, Acthar may target several cell lineages that are relevant in transplantation and maybe a reason of why this medication can work to decrease recurrence after transplantation.

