Recent data has shown an etiologic role of perturbations of the CD40 antigen in recurrent FSGS (4). It is unknown if Acthar would change CD40 in patients with FSGS. As part of our research investigation, we propose to investigate CD40 in kidney biopsies, by immunohistochemistry, and serum of patients, by ELISA. Patients will have one pre-transplant serum sample which will be measured for CD40 by utilizing the CD40 antibody through ELISA. A 2nd blood sample will be obtained at 3 months post transplant, at 6 months post transplant and at 1 year post transplant. This blood will be drawn with standard of care labs, so it would not impose additional blood draws to the patient.

We expect from 7-10 patients a year to meet inclusion criteria.

III. Research Methods and Design

A. Study Type/Design:

Prospective open-label study enrolling renal transplant recipients with the primary native kidney disease of FSGS. This protocol already has an IND exemption as this medication is FDA approved for the treatment of nephrotic syndrome. All subjects will receive Acthar.

B. Endpoints

The primary endpoint is rate of recurrence of FSGS as seen in renal transplant biopsies and in rate of proteinuria.

The secondary endpoints are duration of remission after Acthar treatment (Time Frame: 1 year and 2 years of study follow-up after treatment completion), changes in kidney fibrosis after Acthar treatment and safety and efficacy of Acthar in the post renal transplant population.

C. Patient Recruitment

Preliminary data was previously submitted in the American Transplant Congress 2017. Post renal transplant recipients that developed FSGS were treated with Acthar at the discretion of the investigator. Half of the patients experienced reductions in proteinuria. Prior to the introduction of this medication, developing recurrent FSGS in the renal transplant meant that the renal transplant would likely be lost within a year.

This is a single center pilot study where the target subject number is 20 patients and the target population is primary FSGS patients. By the current data, FSGS should recur in 23-30% of patients. Therefore, it would be expected that at least 4 patients will develop recurrent FSGS after renal transplantation.

After we obtained data from this pilot study we would expect to request funding for a large multicenter study.

Inclusion Criteria:

1. Adult renal transplant recipients with primary FSGS
2. Ability to consent

Exclusion Criteria:

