Sample size: A sample size of 20 data pairs (for example from immediately post-transplant to 12 months post-transplant) achieves 80% power to detect an effect size of change in proteinuria of 0.66 standard deviations with a significance level (alpha) of 0.05 using a two-sided paired t-test. A sample size of 20 produces an exact two-sided 95% confidence interval from 0.087 to 0.491 when the recurrent FSGS proportion is 0.25, i.e. 5/20 patients. If only 4/20 patients develop recurrent FSGS the 95% confidence interval would be 0.057 to 0.437 and if 3/20 patients developed FSGS the 95% confidence interval would be 0.032 to 0.379. This lack of precision in the estimate of the proportion of patients developing recurrent FSGS is due to the small sample size. However, this is a pilot study to determine whether Acthar helps decrease the rate of recurrent FSGS after renal transplantation. The observed rate of recurrent FSGS in patients treated with Acthar will be used to power larger, multicenter studies. We will seek expert opinion from the participating centers regarding expected rates when planning the trial. The outcomes which will be used to plan for a future, larger, more definitive trial will include recurrent FSGS as observed in this pilot study as well as change in proteinuria over time.

Data analysis: Data will be analyzed using two-sided paired t-tests for comparing two time points as well as mixed effects models for multiple time points, to assess changes in proteinuria over time. Other clinical, pathological and laboratory variables may be included in the models to determine whether the change over time is affected by these covariates. Similar methods will be used to model changes in eGFR over time. The observed proportion of patients developing recurrent FSGS will be reported as a proportion with an exact 95% confidence interval. Standard of care labs including CBC, BMP, tacrolimus level, BK PCR plasma, CMV PCR plasma, DSA, Allosure testing and urine protein/creatinine as well as biopsy findings will be reported as summary statistics (means \pm SD, medians (with interquartile range) and proportions as appropriate) at each time point.

All patient information will be de-identified for study purposes.

We will monitor the data and safety measures periodically. We will monitor AEs on a weekly basis.

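### The 80% power for change in proteinuria holds only if all 20 enrolled patients give a complete pair; the plan has no margin for loss

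*Combined protocol and SAP*

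**What the plan says.** The sample-size paragraph in Section III.J reads: "A sample size of 20 data pairs (for example from immediately post-transplant to 12 months post-transplant) achieves 80% power". The target is an "effect size of change in proteinuria of 0.66 standard deviations", tested "with a significance level (alpha) of 0.05 using a two-sided paired t-test". The pair of time points is offered as an example, not fixed.

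Section III.C (Patient Recruitment) says that "the target subject number is 20 patients". No section gives a dropout allowance, a replacement rule or an expected number of evaluable pairs.

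Three places bear on whether pairs may be incomplete:

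- Section I describes the primary endpoint as an intention to "measure proteinuria prior (if patient still makes urine) and after renal transplantation". For that contrast, a missing baseline is provided for in the wording.
- Section II says of recurrence after transplant that "it brings a high risk of graft failure". Section III.C puts recurrence at 23-30% and adds that, before this drug was introduced, a graft with recurrent disease was likely to be lost within a year.
- Section III.I lists seven participant and study stopping criteria, among them withdrawal of consent. It does not say whether outcome data are still collected afterwards.

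The data-analysis paragraph of Section III.J plans paired t-tests for two time points and mixed effects models for several.

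**The concern.** The power calculation counts complete pairs and the recruitment target counts patients, yet both numbers are 20. A paired t-test uses only patients with both values, so the two agree only if nobody is lost. The plan does not say this, and it does not say what power remains if someone is.

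Two things are at stake. A non-significant change in proteinuria could be read against 80% power when the analysed data supported less. Section III.J also says that the change in proteinuria will feed the design of a larger trial, so the planners of that trial need to know how many pairs the estimate and its stated sensitivity rest on.

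**Working it through.** **Inputs.** From Section III.J: n = 20 pairs, standardised change d = 0.66, two-sided alpha = 0.05, paired t-test, stated power 80%. From Section III.C: 20 patients. The documents give no loss rate, so every rate below is an assumption.

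**Formula.** For n complete pairs, the test statistic follows a noncentral t distribution with n − 1 degrees of freedom and noncentrality d√n. Power is the probability that it falls outside ± the 97.5% point of the central t with n − 1 degrees of freedom.

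**The plan's own figure.** With n = 20 the noncentrality is 0.66 × √20 = 2.95 on 19 degrees of freedom, and power is 0.7995. The stated 80% is reproduced. A normal approximation gives 0.839 and a one-sided t-test 0.885, so the plan did use the two-sided t-test that it names.

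**Fewer complete pairs out of 20 enrolled.** The loss is (20 − n)/20. The last column solves the same formula for d at 80% power.

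| Complete pairs | Assumed loss | Power for 0.66 SD | Effect detectable with 80% power |
|---|---|---|---|
| 20 | 0% | 80.0% | 0.66 SD |
| 19 | 5% | 77.7% | 0.68 SD |
| 18 | 10% | 75.2% | 0.70 SD |
| 17 | 15% | 72.4% | 0.72 SD |
| 16 | 20% | 69.4% | 0.75 SD |
| 14 | 30% | 62.7% | 0.81 SD |

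The first lost pair costs 80.0 − 77.7 = 2.3 percentage points.

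**How likely is no loss at all?** If each patient independently had a 5% chance of an incomplete pair, all 20 pairs would be complete with probability 0.95^20 = 0.36. At 10% it would be 0.90^20 = 0.12.

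**Which losses affect which pair.**

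| Route of loss | Pre- to post-transplant (Section I) | Immediately post-transplant to 12 months (Section III.J example) |
|---|---|---|
| No urine before transplant | Yes | No |
| Withdrawal of consent | Yes, if before the later value | Yes, if before month 12 |
| Graft failure after recurrence | Possible | Possible |

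As an illustration of the third route only: Section III.C's 23-30% of 20 is 4.6 to 6 patients, and it states that at least 4 recurrences are expected. Suppose half of 4 to 6 such patients had no usable month-12 value. Then 2 to 3 pairs would be lost, 18 to 17 would remain, and power would be 75% to 72%. The one-half is assumed; the protocol gives no graft-loss rate under treatment.

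**The case against.** The strongest reply is that nothing in the sentence is wrong. It attaches 80% to 20 data pairs, not to 20 enrolled patients whatever their completeness, and the arithmetic is right. That stands: this is not a calculation error.

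A reader might also infer that the protocol expects missing values in the powered comparison, chiefly because some patients no longer make urine. The documents do not support that. Anuria before transplant removes the Section I baseline, but it removes nothing from a pair that starts after transplant. For the example pair, urine protein/creatinine is a standard-of-care test scheduled from the day of surgery through month 12 (Section III.F, Appendix A), and Section III.G takes it from the medical record. Meeting a stopping criterion need not end that collection. Of the seven criteria, only withdrawal of consent plainly implies lost data, and no frequency is given.

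The planned mixed effects models can use patients with incomplete series and may recover part of any loss. This stands too, with two limits. The stated power is for the paired t-test and none is given for the model. And values lost through graft failure would come from patients with recurrence, so they would be unlikely to be missing at random.

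Last, this is an open-label pilot, and no decision rule is tied to the significance of the proteinuria result. That limits the consequence but does not remove the need to state the condition.

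**Conclusion.** The point holds in conditional form. The 80% for 0.66 SD is correct if, and only if, every one of the 20 enrolled patients contributes a complete pair. The plan makes no allowance for loss, while the protocol describes ways in which loss could occur.

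The size depends on a rate that the documents do not give. Under an assumed 5% to 20% loss, power for 0.66 SD is 78% to 69%, and the effect detectable with 80% power is 0.68 to 0.75 SD. These figures assume the paired t-test on complete pairs and a standardised effect that is unchanged among the patients who remain.

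A reader might go further and conclude that the trial will not deliver its stated power. The documents do not establish that. They give no loss rate, the example pair does not depend on pre-transplant urine, and the mixed model may recover some information. The shortfall is possible and its range can be shown, but it is not certain. For a pilot, this is a modest matter that can be put right by restating the power.

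**What to change.** Revise the sample-size paragraph of Section III.J and keep the target at 20 patients:

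1. Name the change from immediately after transplant to 12 months as the powered pair, in place of offering it as an example. This contrast does not depend on pre-transplant urine.
2. State that 80% power for 0.66 SD assumes 20 complete pairs.
3. Give the power and detectable effect for the number of complete pairs expected, with the loss rate labelled as an assumption. For example: with 18 complete pairs (10% loss), power is 75% and the effect detectable with 80% power is 0.70 SD; with 16 (20% loss), 69% and 0.75 SD.

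The cost is a few words and a slightly less favourable stated power. No extra patients or procedures are needed.

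The alternative is to enrol enough patients to expect 20 complete pairs, which is 20/(1 − loss) rounded up: 20/0.95 gives 22, 20/0.90 gives 23 and 20/0.80 gives 25. With 7-10 eligible patients expected a year (Section II), that would lengthen recruitment, and a pilot of this purpose does not require it.

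### If native kidneys are retained, pooling patients with and without residual urine biases the change in protein/creatinine downward and, at the protocol's own recurrence rate, mainly masks recurrence

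*Combined protocol and SAP*

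**What the plan says.** - **Endpoint.** Section I makes it part of the primary endpoint to "measure proteinuria prior (if patient still makes urine) and after renal transplantation and determine the change in proteinuria", alongside recurrence on biopsy. Some patients are thus expected to have native urine. Their number is not given.
- **Design.** "This is an open-label pilot study where all subjects will be treated with the drug, Acthar" (Section I). There is no comparator. FSGS is the native kidney disease of every participant (III.A), and the drug starts at transplantation (III.E).
- **Measure.** Proteinuria is the routine urine protein/creatinine ratio (III.F, III.G, Appendix A). Nothing separates native from graft protein.
- **Analysis (III.J).** The power statement pools all patients: "A sample size of 20 data pairs (for example from immediately post-transplant to 12 months post-transplant) achieves 80% power to detect an effect size". The effect is a "change in proteinuria of 0.66 standard deviations with a significance level (alpha) of 0.05 using a two-sided paired t-test". For the analysis itself, "Data will be analyzed using two-sided paired t-tests for comparing two time points as well as mixed effects models for multiple time points". Adjustment is optional and no covariate is named: "Other clinical, pathological and laboratory variables may be included in the models to determine whether the change over time is affected by these covariates".
- **Use.** III.J says that the observed recurrence and the change in proteinuria will both inform the planning of a larger trial.
- **Silence.** No section mentions native nephrectomy, protein from native kidneys, or residual urine as a stratum or covariate.

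**The concern.** The proteinuria part of the endpoint is meant to reflect the graft. In a patient who was anuric before surgery, urine afterwards comes from the graft alone. In a patient who still made urine and kept the native kidneys, early urine also carries protein from kidneys with FSGS. The pooled test and model treat these two quantities as one.

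If the native part declines during follow-up, those patients show a fall that has nothing to do with the graft. In the pooled mean this offsets a rise in patients whose disease recurs. If nobody recurs, it can appear as an improvement. With a single arm and the drug started at surgery, the design cannot separate native decline from a drug effect. The resulting effect size would then feed the next trial.

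**Working it through.** **1. The plan's own figure.** Paired t-test, n = 20, effect 0.66 SD, two-sided alpha 0.05. Noncentrality = 0.66 × √20 = 2.95 on 19 df, critical value 2.093. Power is 79.9%, against 80% stated. The arithmetic is right. The question is what the change measures.

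**2. Inputs for the bias.** From the protocol: 20 pairs, the test, and expected recurrence of 23-30% (Section II, III.C), taken as 25%. Everything else is assumed, because the documents give no figure:
- graft ratio 0.2 × exp(N(0, 0.5)) at each time;
- native protein g = 1, 2 or 4 g/day at the first sample and none at month 12, divided by creatinine excretion of 1.2 g/day, with the same lognormal spread;
- share f of patients with residual urine, varied;
- in recurring patients, a rise r of 1-3 g/g by month 12, with the same spread.

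**3. Mean change by hand, f = 20%.** The spread multiplies means by exp(0.125) = 1.133.
- Native fall = 0.20 × (g/1.2) × 1.133 = 0.19 g/g at g = 1 and 0.76 g/g at g = 4.
- Recurrence rise = 0.25 × r × 1.133 = 0.28 g/g at r = 1 and 0.85 g/g at r = 3.
- Net change for r = 1: +0.09 (g = 1) to -0.47 (g = 4). For r = 3: +0.66 to +0.09.

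An average rise of 0.28-0.85 g/g is reduced, nearly cancelled or reversed.

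**4. Simulated test results, no drug effect.**

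| Share with residual urine | Recurrence | Significant rise | Significant fall |
|---|---|---|---|
| 0% | 25%, rise 1-3 g/g | about 53-60% | about 0% |
| 20% | 25%, rise 1-3 g/g | about 1-27% | about 0.2-10% |
| 30% | 25%, rise 1-3 g/g | – | about 0.4-34% |
| 10% | none | – | about 7-10% |
| 20% | none | – | 35-39% |
| 30% | none | – | 66-76% |
| 50% | none | – | 97-99% |

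The nominal rate of a false fall is 2.5%. At a 50% share with 25% recurring, false falls range from 1-34% (rise of 3 g/g) to 18-88% (rise of 1 g/g).

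**5. Sensitivity, 20% share, no recurrence.** If native protein only halves by month 12, false falls are 27-39%. With a log-transformed ratio and only half fading, 10-14%.

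**6. A second model.** Native fall lognormal with mean 1-3 g/g and CV 0.7, noise SD 0.5 g/g, 25% with residual urine. With 25% recurring at a mean rise of 3 g/g, the chance of a significant rise drops from 47% to 2-15%, and false falls are 0.2-2%. Without recurrence, false falls are 26-46%. The pattern is the same.

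**7. Reach of the 10% row.** It concerns false falls without recurrence. By the formula in step 3, a 10% share still takes 0.09-0.38 g/g off a mean rise of 0.28-0.85 g/g.

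**The case against.** - **A reader might infer that the plan is likely to manufacture an Acthar effect.** The no-recurrence rows invite this, but the documents do not support it. Without a drug effect, the protocol expects 23-30% of patients to recur, at least 4 of 20, and Section II describes heavy proteinuria when they do. Under that null a false fall is uncommon at a 20% share. It becomes frequent only with a larger share and a small rise. This objection stands, and it makes masking the main harm.
- **The driving inputs are outside the documents.** Retained native kidneys are inferred from silence. The share with residual urine, the native protein level and its fading are all assumed, and so is the rise on recurrence, which could be smaller once recurrence is treated (III.H). This stands for the size of the bias, not for the exposure to it.
- **It is only a matter of baseline.** The pair in III.J is an example, and Appendix A has many visits, so a later baseline could avoid most of an early washout. This stands in part. No baseline is fixed, the speed of fading is unknown, and the mixed model may use the early values anyway. A pre-transplant baseline is native protein only.
- **The consequence is limited.** The biopsy samples the graft, and an uncontrolled pilot cannot attribute a change to the drug in any case. Both are true, but III.J still carries the proteinuria change into the next trial.

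**Conclusion.** The concern holds in limited form. III.J pools patients whose urine is graft-only with patients whose early urine may be mixed, and no prespecified term separates them. If native kidneys are retained and their protein declines, the pooled change is biased downward.

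Under the assumed inputs at a 20% share, the main effect at the protocol's recurrence rate is a loss of ability to see the rise, from about 53-60% to about 1-27%. A false significant fall reaches about 35-40% at that share only if almost nobody recurs. With a share of 10% or less and no recurrence the bias is small, and in anuric patients it is nil.

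Three stronger statements are not supported: that native kidneys are known to be retained, that a spurious benefit is the expected result, or that the stated 80% power is miscalculated. Strictly, the ratio is a creatinine-weighted mix of the two sources, not a plain sum. The biopsy-based recurrence proportion and its exact interval are unaffected.

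**What to change.** In III.J:

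1. Report the paired change and the proteinuria trend separately for patients anuric at screening and for those still making urine.
2. Prespecify residual-urine status and its interaction with time as a model term, in place of the optional covariates. The screening protein/creatinine, already scheduled in Appendix A, can serve instead and carries more information than yes/no.
3. State that only the anuric stratum is read as graft proteinuria. Do not define a set of values taken after native output has stopped: once the graft works, nothing scheduled identifies that point.
4. State that the pooled change will not be carried into planning of the larger trial as an Acthar effect.

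The cost is SAP wording, a recorded urine status at screening and one stratified table, with no new samples. The strata are small. At 0.66 SD the anuric stratum has 75% power with 18 pairs, 66% with 15, 55% with 12 and 46% with 10, so the results should be presented as estimates with wide intervals.
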